## 4.1.2 Exclusion Criteria

- 1. Body Mass Index (BMI) in 99th percentile or above.
- Current or lifetime diagnosis of epilepsy, major depressive disorder, bipolar disorder, schizophrenia or related disorder, personality disorder, Tourette's disorder, or psychosis not otherwise specified.
- 3. Currently meeting DSM-5 criteria for autism spectrum disorder, pervasive developmental disorder, obsessive compulsive disorder, post-traumatic stress disorder, or any other anxiety disorder as primary diagnosis.
- 4. Use of anticonvulsants including carbamazepine and valproic acid, antidepressants, mood stabilizers including lithium, benzodiazepines, cholinesterase inhibitors or any drug known to inhibit CYP2D6 activity within two weeks of Visit 2.

- 5. Use of herbal supplements within one week of Visit 2.
- 6. Known or suspected intelligence quotient (IQ) < 70.
- 7. Unstable endocrinological or neurological conditions which confound the diagnosis or are a contraindication to treatment with antipsychotics.
- 8. Suicidality, defined as either active suicidal plan/intent or active suicidal thoughts in the six months before the Screening Visit or more than one lifetime suicide attempt.
- 9. Pregnancy or refusal to practice contraception during the study (for female subjects of childbearing potential).
- 10. Substance or alcohol use during the last three months.
- 11. Urine drug test at screening that is positive for alcohol or drugs of abuse.
- 12. Known allergy or sensitivity to molindone hydrochloride.
- 13. Any reason which, in the opinion of the Investigator or the Sponsor, would prevent the subject and subject's caregiver from participating in the study or complying with the study procedures.
- 14. Use of an investigational drug or participation in an investigational study within 30 days prior to Visit 2.

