# 4.4 **Prohibited Medications:**

Subjects may not be on any prohibited medication while on study as indicated in the Inclusion/Exclusion Criteria. These medications include:

- α 2- adrenergic agonists (e.g. clonidine and guanfacine) used for any other reason except for monotherapy treatment for ADHD
- Anti-psychotics including aripiprazole, risperidone, quetiapine, and ziprasidone
- Anticonvulsants including carbamazepine and valproic acid, antidepressants, mood stabilizers including lithium, benzodiazepines, cholinesterase inhibitors or any drug known to inhibit CYP2D6 activity
- Herbal supplements

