# 4.5 **Concomitant Medication**

The dose of the ongoing ADHD medication will not be adjusted during the study, starting at Visit 1. No additional concomitant medications are allowed during the study, with the following exceptions:

- Chronic medication for conditions not related to ADHD or IA that are allowed by Investigator at Screening
- Nutritional supplements (e.g. multivitamins, fish oil)
- Emla or other numbing cream for PK venipuncture
- Benztropine is permitted for the treatment of emerging EPS at a starting dose of 0.5mg BID up to a range of 1 to 4mg/day. Lorazepam (1 to 2 mg per dose not to exceed three times daily) and

clonazepam (0.25 to 1 mg per dose not to exceed twice daily) will also be permitted to treat emerging EPS.

- Common over-the-counter (OTC) therapies for minor transient ailments (e.g. acetaminophen for headache, ibuprofen for fever) will be allowed without exception.
- Treatment for AEs other than EPS or minor transient ailments is only permitted in consultation with the Medical Monitor.

All concomitant medications will be recorded in the eCRF.

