# 5.4.3 Management of Treatment-Emerging EPS

If a subject experiences treatment-emerging EPS (including akathisia, dystonia, Parkinsonism, or tardive dyskinesia), benztropine will be permitted at a starting dose of 0.5 mg BID up to a range of 1 to 4 mg/day. Lorazepam (1 to 2 mg per dose not to exceed three times daily) and clonazepam (0.25 to 1 mg per dose not to exceed twice daily) will also be permitted to treat emerging EPS.

A positive finding on an EPS safety assessment scale (Barnes Akathisia, Simpson-Angus, AIMS) does not necessarily equate to an EPS event. Investigators should evaluate positive findings on the EPS safety assessment scales and integrate them into a global clinical observation to determine if an AE of EPS should be recorded.

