5.4 Safety Variables

5.4.1 *Medical History and Adverse Events (AEs)*

AEs that occur on/after signing ICF will be recorded on the AE CRF. Medical history and AEs will be coded for preferred term (PT) and system organ class (SOC) using Medical Dictionary for Regulatory Activities (MedDRA). AEs are evaluated by the investigators for seriousness, relationship, and severity.

5.4.2 *Prior, Concomitant, and Prohibited Medications*

Prior medications and concomitant medications will be extracted from the Prior/Concomitant Medication CRF. Medications taken prior to Study Day 1 will be considered as prior medications and medications taken on or after Study Day 1 will be considered as concomitant medications. Prior and concomitant medications will be coded using WHO Drug Dictionary (WHODD) for PT and Anatomical Therapeutic Chemistry (ATC) classification.

Prohibited medications include, but are not limited to,

- α_2 -adrenergic agonists (e.g. clonidine and guanfacine) used for any other reason except for monotherapy treatment for ADHD
- Anti-psychotics including aripiprazole, risperidone, quetiapine, and ziprasidone
- Anticonvulsants including carbamazepine and valproic acid, antidepressants, mood stabilizers including lithium, benzodiazepines, cholinesterase inhibitors or any drug known to inhibit CYP2D6 activity
- Herbal supplements

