7.1.3 Intent-to-treat (ITT) Population

The intent-to-treat population will include all subjects who received at least 1 dose of study drug and at least 1 valid post-randomization assessment of frequency of IA behaviors based on IA diary entry. Subjects will be analyzed according to the treatment they were randomized to.

7.1.4 *Per Protocol (PP) Population*

The per protocol population will include all of the subjects in the ITT population who completed the treatment period (Completed Maintenance Visit 6) with 80% diary completion compliance and who did not have major protocol deviations. Diary compliance is calculated as

diary compliance = $\frac{\text{number of days diary completed within the treatment period}}{\text{Number of treatment days}} \times 100\%$

Detailed specification of the PP population will be provided prior to the database lock for the final analysis.

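### Protocol 4.4 and SAP 5.4.2 prohibit benzodiazepines without exception while protocol 4.5 and 5.4.3 permit two of them for emerging EPS, so the SAP as written would report permitted treatment as a prohibited-medication deviation

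*SAP*

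**What the plan says.** **The prohibition.** Protocol 4.4 opens with "Subjects may not be on any prohibited medication while on study as indicated in the Inclusion/Exclusion Criteria" and then names benzodiazepines as a class. SAP 5.4.2 carries the same list, including "mood stabilizers including lithium, benzodiazepines, cholinesterase inhibitors or any drug known to inhibit CYP2D6 activity". Neither version mentions EPS, and protocol 4.4 does not refer to 4.5 or 5.4.3.

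**The permission.** Protocol 4.5 bars additional concomitant medication apart from a list of exceptions. After benztropine, that list gives "Lorazepam (1 to 2 mg per dose not to exceed three times daily) and" then "clonazepam (0.25 to 1 mg per dose not to exceed twice daily) will also be permitted to treat emerging EPS". Protocol 5.4.3, on managing treatment-emerging EPS, names the same two drugs, which "will also be permitted to treat emerging EPS". The SAP contains no equivalent statement.

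**The use made of the list.** SAP 7.4 makes prohibited medication a type of protocol deviation. SAP 7.7.2 calls for a separate listing of subjects who received it (Listing 16.2.1.9.3). SAP 7.1.4 limits the per-protocol set to ITT subjects who completed Visit 6 with 80% diary compliance and "who did not have major protocol deviations". The same section defers the detailed per-protocol specification to a point before database lock.

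**The concern.** A programmer who builds the prohibited-medication flag from SAP 5.4.2 will flag every benzodiazepine. A child given lorazepam or clonazepam exactly as protocol 4.5 allows would then be reported as having taken a prohibited drug.

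Two things are at stake. The first is the accuracy of the deviation classification and the prohibited-medication listing. The second, which is conditional, is the make-up of the per-protocol set. EPS is the side effect that this trial monitors for an antipsychotic, with three rating scales (protocol 3.1) and special-interest event reporting (protocol 5.4.2.2). Children treated for it would be expected mainly on 36 mg. Removing them for that treatment would be an exclusion related to the assigned drug, and it would take out children who tolerated the drug less well.

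**Working it through.** The point rests on comparing the text; no sample-size or power figure depends on it.

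| Place | Benzodiazepine rule | Period | EPS exception |
|---|---|---|---|
| Protocol 4.1.2, criterion 4 | Prior use excludes | "drug known to inhibit CYP2D6 activity within two weeks of Visit 2" | Not applicable |
| Protocol 4.4 | Class prohibited | While on study | None |
| SAP 5.4.2 | Class prohibited | No limit stated | None |
| Protocol 4.5 | Two drugs permitted | During the study | Yes |
| Protocol 5.4.3 | Same two drugs permitted | On emergence of EPS | Yes |

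Following one child on study who is given lorazepam for EPS:

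1. Protocol 4.5 and 5.4.3: the use is permitted.
2. SAP 5.4.2: the drug belongs to a prohibited class.
3. SAP 7.7.2: the child appears in the prohibited-medication listing. No further condition is attached.
4. SAP 7.4: the use falls under a named deviation type. The deviation listing and table show major deviations only, so the child appears there only if the deviation is classed as major.
5. SAP 7.1.4: the child leaves the per-protocol set only if the deviation is major **and** the child would otherwise have qualified by completing Visit 6 with adequate diary compliance.

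Steps 1 and 2 conflict as written. Step 3 follows directly. Steps 4 and 5 depend on a definition of major that the SAP does not give. Appendix 1, on per-protocol exclusion criteria, shows only its heading in the text available.

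**Is lost power a concern?** The documents give no rate of benzodiazepine use for EPS, overall or by arm, so the loss can only be illustrated. Start from the plan's own figure, difference 15 and SD 34.83 (protocol 6.10):

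- p = Φ(15 / (34.83 × √2)) = 0.6196
- n per arm = (1.960 + 1.282)² / (6 × (p − 0.5)²) = 122.4, which reproduces the stated 122.
- Power = Φ(√(12·n₁n₂/(n₁+n₂)) × (p − 0.5) − 1.960). With 122 per arm this is 89.9%.

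Assumed losses, not taken from the documents:

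- 1% of 36 mg and 0% of placebo: 122 × 0.01 = 1.2 and 0 children; power 89.8%.
- 10% of 36 mg and 2% of placebo: 122 × 0.10 = 12.2 and 122 × 0.02 = 2.4 children; power 88.0%.

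The 122 per arm is only a convenient start, since the real per-protocol arms will differ in size. Across this range the power loss is small. What matters is who would be removed and how the use is labelled.

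**The case against.** The strongest reply is that protocol 4.5 is the specific exception to a general rule. It names the drugs and the reason, and 5.4.3 agrees with it. Protocol 4.4 ties its list to the entry criteria, where benzodiazepine use is limited only around Visit 2, and never mentions EPS. Protocol 6.6 speaks of disallowed medication, and SAP 7.7.2 plans a table of allowed medication apart from the prohibited listing, so a careful coder would check 4.5. The SAP supersedes the protocol's statistical methods, not its medication permissions.

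This makes a drafting gap more likely than a deliberate second rule, but it does not cure the text. The exceptions in 4.5 qualify the ban stated in 4.5, not the list in 4.4. Protocol 4.4 does write in an exception where it wants one, for alpha-2 agonists used as ADHD monotherapy, and gives none for benzodiazepines. The SAP holds only the prohibition.

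Two stronger readings are tempting, and the documents do not support them.

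- A reader might infer that sites have two opposite instructions for managing EPS. The two sections that address EPS treatment agree with each other; the conflict is with a general list.
- A reader might infer that the per-protocol set will be thinned selectively by some number of percentage points. No rate is given, *major* is undefined, and children who stop before Visit 6 are already out. Benztropine, the first EPS drug named, is not on the prohibited list, so children given it alone are unaffected.

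**Conclusion.** Wrong as written, minor. The conflict between protocol 4.4 with SAP 5.4.2 on one side and protocol 4.5 with 5.4.3 on the other stands in the current text, and the SAP follows only the prohibition. Its certain effect, if the SAP is applied literally and any child receives one of the two drugs, is that permitted treatment is listed as prohibited-medication use and falls under a deviation type.

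Removal from the per-protocol set is possible but conditional on how *major* is defined, and it would reach only children who otherwise qualify. That the active arm would lose more is an inference from the drug class, not a documented rate.

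The per-protocol analysis is supplementary (SAP 7.8.3). The primary mITT analysis and its ITT repeat exclude nobody for deviations, so the primary estimate, its type I error and its power are not affected.

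**What to change.** 1. Reconcile protocol 4.4 with 4.5 and 5.4.3, so that one rule on benzodiazepines during the study can be read from all three. This point takes no position on which rule is right.
2. Apply the reconciled rule in SAP 5.4.2, in the prohibited-medication deviation category of SAP 7.4 and in the listing under SAP 7.7.2.
3. In the per-protocol specification, state before unblinding that use the reconciled protocol permits is not a major deviation.

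The cost is about one sentence in the protocol, one in the SAP and a coding flag by drug and indication. Because the per-protocol specification is still to be written, the third step needs only a line in a document already planned. Settled after unblinding, the same choice could look driven by the results.

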5.4.3 Clinical Laboratory Tests (Hematology, Chemistry, and Urinalysis)

Laboratory tests will be converted to follow the International System (SI) units. Laboratory tests will be collected at Visits 1, 3, 6, and 7. The tests include hematology, serum chemistry and urinalysis panels. Laboratory values will be categorized according to the appropriate laboratory reference ranges.

5.4.4 Vital Signs, Height and Weight

Vital signs include body temperature, heart rate, respiratory rate, systolic blood pressure, and diastolic blood pressure. They will be collected at Visits 1 and 7. Subject height, weight, and BMI will be collected at Visits 1 and 3 - 7.

5.4.5 *12-Lead ECG*

The following ECG variables will be collected at Visits 1, 4, and 6: HR (heart rate), PR (respiratory rate), QRS interval, QT interval, and QTcF (QT interval corrected using the Fridericia's method).

5.4.6 *Physical Examinations*

Physical examinations will be conducted at Visit 1 and Visit 6. Clinically significant findings will be reported as adverse events.

5.4.7 Columbia Suicide Severity Rating Scale (C-SSRS)

The C-SSRS (Protocol Appendix 10.6) is a questionnaire assessing suicidal ideation and behavior at baseline and since last visit. This assessment will be conducted at Visits 1, and 3 - 7. The following outcomes are C-SSRS categories and have binary responses (yes/no).

Category 1 – Wish to be dead Category 2 – Non-specific Active Suicidal Thoughts Category 3 – Active Suicidal Ideation with Any Methods (Not Plan) without Intent to Act Category 4 – Active Suicidal Ideation with Some Intent to Act, without Specific Plan Category 5 – Active Suicidal Ideation with Specific Plan and Intent Category 6 – Preparatory Acts or Behavior Category 7 – Aborted Attempt Category 8 – Interrupted Attempt Category 9 – Actual Attempt (non-fatal) Category 10 – Completed Suicide Three composite binary endpoints and one severity score are derived from the above categories.

Suicidal ideation: A "yes" answer at any time during treatment to any one of the five suicidal ideation questions (Categories 1-5) on the C-SSRS.

Suicidal behavior: A "yes" answer at any time during treatment to any one of the five suicidal behavior questions (Categories 6-10) on the C-SSRS.

Suicidal ideation or behavior: A "yes" answer at any time during treatment to any one of the ten suicidal ideation and behavior questions (Categories 1-10) on the C-SSRS.

Suicidal Ideation score: The maximum suicidal ideation category (1-5 on the C-SSRS) present at the assessment. Assign a score of 0 if no ideation is present.

5.4.8 Infrequent Behaviors Checklist

The infrequent behaviors checklist is a checklist of 15 behaviors that (along with the 15 IA Diary behaviors) were qualitatively linked to IA during the development of the IA diary. These behaviors include teasing, spitting, biting, weapons, ripping, breaking, vandalizing, destroying, fire setting, hitting animal, kicking self, kicking animal, severe injury self, severe injury others, severe injury animal. Caregivers will be asked which, if any, of these behaviors have been observed since the patient's last visit. This assessment will be administered at Visits 3 – 6 by the site coordinator.

5.4.9 *Extrapyramidal symptoms (EPS) scales*

The EPS symptom and neuroleptic malignant syndrome will be evaluated using the Simpson-Angus scale (Protocol Appendix 10.8), the Barnes Akathisia scale (Protocol Appendix 10.9), and the Abnormal Involuntary Movement scale (AIMS) (Protocol Appendix 10.10). The Simpson-Angus scale is a 10-item rating scale, consisting of 1 item measuring gait, 6 items measuring rigidity, and 3 items measuring glabella tap, tremor and salivation. The Barnes Akathisia scale is a rating scale for drug-induced akathisia. It includes Objective Akathisia, Subjective Awareness of Restlessness, Subjective Distress Related to Restlessness, and Global Clinical Assessment of Akathisia subscales. Additionally, total score will be calculated by summing up the Objective and two Subjective scale scores (Barnes 1989). The objective and two subjective symptoms are rated on a 4-point scale ranging from 0 to 3. The global clinical assessment is rated on a 5-point scale ranging from 0 to 4. The AIMS test is a rating scale used to measure tardive dyskinesia (Munetz 1988). It includes 12 items to rate involuntary movements of various areas of the subject's body. These assessments will be administered at Visit 3 and all subsequent visits.

6 **STATISTICAL METHODS**

6.1 General Methodology

All statistical analyses will be conducted using SAS Version 9.4 or later on the Microsoft[®] Windows Operating System.

All tabulations of results will include summaries for the three treatment groups: SPN810 36mg, SPN810 18mg and placebo, however, statistical test will only include SPN810 36mg and placebo.

Continuous data will be summarized using n (number of subjects with non-missing observations), mean, median, standard deviation (SD), minimum value, and maximum value. Categorical data will be summarized using the frequency count and percentage (n, %) of subjects in each category. Number of subjects with non-missing values or number of subjects with missing values (e.g., Not Done) will be presented, where appropriate. Subjects with missing values will not contribute to the denominator of percentage calculations. Counts of zero in any category will be presented without percentage.

Treatment differences will be evaluated as SPN-810 dose minus placebo. Unless otherwise specified, all statistical hypothesis tests will be 2-sided with a significance level of α =0.05. All confidence interval will be calculated 2-sided from the unadjusted 5% significance level. P-values will be reported to 4 decimal places. P-values <0.0001 will be presented as "<0.0001". Similarly, p-values >0.9999 will be presented as ">0.9999"

The precision rules for the presentation of summary statistics will be:

- Sample size (n, N) and number of missing responses (if displayed) Integer
- Mean, median, percentiles, and confidence interval One additional decimal place than reported/collected
- Standard deviation Two additional decimal places than reported/collected
- Minimum, maximum Same number of decimal places as reported/collected
- Ratios two decimal places
- Percentages one decimal place generally, or two decimal places for <0.1%

The data summaries will be accompanied by individual subject data listings. All data available from diary, eCRF, and external transfer (labs) will be listed and will include relevant and pertinent subject information, e.g., treatment, center, age/gender/race, and study day. The listings will be sorted in the order of treatment group, unique subject ID, and assessment date/time and assessment name. The unique subject ID consists of 3-digit study number followed by digit site

number and digit subject number separated by hyphen (e.g.,

For each summary table, a supporting listing will be identified in the footnote.

Dates will be presented in the ISO-8601 format YYYY-MM-DD. Times will be displayed in 24-hour clock format. Numbering for tables, figures and listings will follow ICH E3 Guidelines.

Alternative methods of analysis of the data may be considered prior to un-blinding when some of the assumptions underlying the proposed analyses not be met. However, the reason for any departure from the planned approach and methods will be fully documented as an amendment to the SAP or in the clinical study report.

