# 5.4 Safety Assessments

Safety assessments will consist of monitoring of and recording of all concomitant medications and AEs, clinical laboratory tests, measurement of vital signs and 12-lead ECGs, suicidality monitoring, and the performance of physical examinations at visits designated in the Schedule of Visits and Procedures (Table 1).

Assessment of possible neurological side effects and EPS will be performed using the Simpson-Angus scale, the Barnes Akathisia scale and the AIMS. A positive rating or finding on the safety scale will be captured as an AE at the discretion of the Investigator.

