# 5.4.2.2 Other Events Requiring Immediate Reporting

The Investigator must report a **pregnancy** that occurs in a subject during a clinical study to the Drug Safety Contact within 24 hours of first becoming aware of the event. Pregnancy should be reported on a Pregnancy Report Form. The Investigator should discuss the case with the Medical Monitor; the Investigator must follow any pregnant subject for 3 months after the child is born. The Investigator must complete a Pregnancy Outcome Form as a follow up. Any AEs concerning the pregnancy of the subject during pregnancy or the child after birth must be documented and reported to the Sponsor.

Treatment-emerging **EPS** (e.g. akathisia, dystonia, Parkinsonism, tardive dyskinesia) and neuroleptic malignant syndrome should be reported to the Drug Safety Contact person(s) by completing the Adverse Event of Special Interest (AESI) eCRF in EDC. Should the site be unable to access EDC, a paper AESI form must be completed and sent to **Drug** Safety by email or fax within 24 hours of first becoming aware of the event. Once EDC becomes available the site must complete AESI eCRF in EDC. EPS incidence will be summarized and shared with study Investigators throughout the trial.

**Overdosage** of molindone presumably may be manifested by severe EPS and sedation. Coma with respiratory depression and severe hypotension resulting in a shock-like syndrome could occur. In the event of a suspected overdose, the parent or legal representative should be instructed to call 911 or their local poison control center

Symptomatic, supportive therapy should be the rule. Gastric lavage is indicated for the reduction of absorption of molindone which is freely soluble in water. Since the adsorption of molindone by activated charcoal has not been determined, the use of this antidote must be considered of theoretical value.

Emesis in a comatose patient is contraindicated. Additionally, while the emetic effect of apomorphine is blocked by molindone in animals, this blocking effect has not been determined in humans.

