3.5 Determination of Sample Size

The original sample size was based on the results from the Phase 2 study. It was assumed that the average treatment difference between SPN-810 dose groups and placebo is 15 with a common standard deviation (SD) =27.3. A sample size of 77 subjects per arm (1:1:1 allocation ratio) would yield 90% power to detect a non-zero difference between the median of 18 mg or 36 mg dose group and the placebo using the Wilcoxon rank-sum test with a 2-sided significance level of alpha=0.05.

After the interim analysis for Study 810P301, the 18 mg dose arm was discontinued for randomization. Subjects planned to be randomized to the 18 mg arm were re-randomized to the 36 mg or placebo arms at a 2:1 allocation ratio. A blinded review of the 810P301 data indicates that the SD for the interim data was actually 34.83 instead of the protocol assumed 27.3. This new SD leads to a total sample size of 306 (adjusted for 20% attrition) subjects. Approximately 167 subjects were randomized prior to the implementation of the 2:1 randomization. It follows that 139 subjects would be randomized in a 2:1 ratio of 36 mg to following the re-calculation of sample size with the new SD.

The sample size was calculated using the nQuery Advisor Software, Version 7.

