7.2 Analysis for the Discontinued Treatment Arm

As stated in Section 3.5, the enrollment for the 18 mg arm was discontinued after the interim analysis for Study 810P301, a study separate from this one. As a result, there will be no formal hypothesis tests and statistical comparison between the 18 mg arm and placebo for any efficacy endpoints. However, for completeness in the presentation, 18 mg arm will remain in the table with summary statistics presented.

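### The safety tables set an 18 mg arm that enrolled only early beside whole-study 36 mg and placebo arms, so a change over time in EPS recording would read as a dose difference

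*SAP*

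**What the plan says.** SAP 6.1 requires that "All tabulations of results will include summaries for the three treatment groups: SPN810 36mg, SPN810 18mg and placebo", and adds in the same sentence that the "statistical test will only include SPN810 36mg and placebo". SAP 7.2 records that "the enrollment for the 18 mg arm was discontinued after the interim analysis for Study 810P301", and that "for completeness in the presentation, 18 mg arm will remain in the table with summary statistics presented". SAP 3.5 gives the timing: "Approximately 167 subjects were randomized prior to the implementation of the 2:1 randomization", leaving 139 to be randomised afterwards.

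The safety population (SAP 7.1.1) is all randomised and dosed children with a post-randomisation safety measurement. Safety summaries (SAP 7.9) are by treatment group, and adverse events also by on-treatment period. None is restricted to children randomised over the same time or carries a note that 18 mg enrolment stopped early. Table 14.3.1.6 orders preferred terms by incidence in the two active doses combined (SAP 7.9.1).

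On EPS, Protocol 5.4 says that "A positive rating or finding on the safety scale will be captured as an AE at the discretion of the Investigator", and Protocol 5.4.2.2 says that "EPS incidence will be summarized and shared with study Investigators throughout the trial".

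**The concern.** The three columns cover different stretches of calendar time. All 18 mg children were randomised before the arm closed; more than half of the 36 mg children and about half of the placebo children came later. That would not matter if adverse events were recorded in the same way throughout. For EPS the protocol itself supplies a route for change: recording depends on judgement, and the people exercising that judgement are told the running incidence. A rise or fall in the readiness to record EPS would then appear in the table as a difference between doses, or would mask one.

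At stake is how the 18 mg safety column is read. Children enter the open-label extension at 18 mg/day (Protocol 3.2 and 3.2.3), so readers will have reason to look at it. SAP 7.2 rules out formal comparison of 18 mg for efficacy endpoints, but gives no caution about reading its safety rates against the other columns.

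**Working it through.** **Inputs.** About 167 randomised before the change and 139 after (SAP 3.5); 1:1:1 before (SAP 3.3.3); total 306 (SAP 3.5, Protocol 6.10).

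**The plan's own figures.** With a difference of 15 and SD 34.83, P = Φ(15 / (34.83 × √2)) = 0.6196. The Noether formula for the Wilcoxon test gives (1.960 + 1.282)² / (6 × 0.1196²) ≈ 122 per arm, as stated. Then 2 × 122 / 0.80 = 305 (stated 306), and 306 − 167 = 139 exactly.

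**Arm by period.** Early, each arm has 167 / 3 = 55.7. The later allocation can be read in two ways.

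- 2:1 for everyone, as SAP 3.5 puts it ("It follows that 139 subjects would be randomized in a 2:1 ratio of 36 mg"): 139 × 2/3 = 92.7 on 36 mg and 139 × 1/3 = 46.3 on placebo.
- Only the former 18 mg slots are split 2:1, as SAP 3.3.3 and Protocol 4.3.4 put it. The ratio is then (1/3 + 2/9):(1/3 + 1/9) = 5:4, giving 77.2 and 61.8.

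| Reading | 18 mg: total (early share) | 36 mg: total (early share) | Placebo: total (early share) |
|---|---|---|---|
| 2:1 | 55.7 (100%) | 148.3 (37.5%) | 102.0 (54.6%) |
| 5:4 | 55.7 (100%) | 132.9 (41.9%) | 117.4 (47.4%) |

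Protocol 6.10 instead expects about 121 on placebo. That leaves 306 − 55.7 − 121 = 129.3 on 36 mg, with early shares of 46% (placebo) and 43% (36 mg). The conclusion does not depend on the reading.

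**Spurious difference.** Let D be the late minus the early recorded rate, equal in all arms (no dose effect). Two columns then differ by D times the difference in their early shares:

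- 18 mg versus 36 mg: (1 − 0.419) D to (1 − 0.375) D = 0.58 D to 0.63 D
- 18 mg versus placebo: (1 − 0.546) D to (1 − 0.474) D = 0.45 D to 0.53 D
- 36 mg versus placebo, for scale: 0.06 D to 0.17 D

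**Illustration.** The documents give no EPS rate by period, so these rates are assumed.

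| Early → late, all arms | 18 mg | 36 mg | Placebo |
|---|---|---|---|
| 10% → 15% | 10.0% | 12.9–13.1% | 12.3–12.6% |
| 10% → 5% | 10.0% | 6.9–7.1% | 7.4–7.7% |

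The first row looks like a dose gradient and the second like its reverse. Neither contains a dose effect.

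**After the change.** Among the 167 early children the arms are about 56, 56 and 56, all 100% early. The difference in early shares is zero, and so is the spurious term, whatever D is.

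**The case against.** The strongest reply is that the 18 mg column is only a display. No 18 mg contrast is planned, formal tests exclude the arm, and no p-value or type I error is touched. That stands, and it limits the weight of the point.

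The drift is also hypothetical. The documents do not say whether the shared EPS incidence is pooled or by arm, or that it alters recording, and nothing ties a change to the date the arm closed. That stands too: the documents show a route, not a rate.

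On the assumed 10% to 15% step, the bias is small against sampling error. The spurious 18 mg versus placebo difference is 2.3 to 2.6 points, with a standard error of 5.1 to 5.2 points. Restricting placebo to the early children removes the bias but raises the standard error to √(2 × 0.10 × 0.90 / 55.7) = 5.7 points, so root mean squared error hardly moves (5.6 to 5.7 before, 5.7 after). This would tell against replacing the whole-study columns. It does not tell against adding columns, since both views then stand and the imbalance in enrolment period is removed by design.

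Listings carry assessment dates and the randomisation schedule is itself listed, so the split could be made later if a signal appeared. But then it would be post hoc. The one figure whose title mentions stage (Figure 14.2.1.1) is an efficacy figure and leaves the term undefined.

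Three stronger inferences are tempting and are not supported:

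- That 18 mg is the only within-trial information on dose and EPS. Protocol 6.13.1 plans TEAE incidence by dose at first occurrence. SAP 7.9.1 does not repeat that table, but tabulates events by titration, maintenance and taper period, which also bears on dose.
- That the drift reaches the EPS-scale tables. The route is the decision whether a finding becomes an adverse event. Simpson-Angus, Barnes and AIMS scores are taken at Visit 3 and every later visit, and are tabulated whether or not an event is recorded (SAP 5.4.9 and 7.9.7).
- That a pooled active-dose rate is planned. In SAP 7.9.1 the combined group is only the sort key for Table 14.3.1.6; it sets row order, not a reported rate.

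**Conclusion.** The point holds as one of presentation. In the planned adverse event tables, 18 mg is not compared with children randomised over the same time. Any change of D points in EPS recording between the two periods would show as about 0.6 D against 36 mg and about 0.5 D against placebo, with no dose effect.

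This rests on the counts in SAP 3.5, on 1:1:1 allocation before the change, and on a common D across arms. It also takes the re-allocation to apply to children not yet randomised, as SAP 7.2 indicates; the protocol synopsis speaks of re-randomising subjects in the 18 mg arm, and the two should be reconciled. Whether D differs from zero, and in which direction, cannot be known from the documents.

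A reader might infer that 36 mg versus placebo is compromised as well. It is not at issue here: both arms enrolled in both periods, and only the change of ratio separates them. The formal efficacy tests do not use EPS recording. This is a cheap improvement, not a threat to the trial's conclusions.

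**What to change.** In SAP 7.2 and 7.9.1, for the overall TEAE table and the EPS/AESI adverse event tables:

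- Add 36 mg and placebo columns limited to children randomised while the 18 mg arm was open, and name these as the comparators for 18 mg.
- Keep the whole-study 36 mg and placebo columns.
- Footnote the 18 mg column to say that its enrolment stopped early and that whole-study columns include later children.
- Sort Table 14.3.1.6 by incidence on 36 mg instead of in the combined active group.

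The EPS-scale tables need no change on this ground. The cost is a few extra columns built from the randomisation schedule already held, and lower precision in the concurrent comparison, with about 56 children per arm.
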